4.4.6.4. Trial Intervention Compliance

During the study, the field monitor will visit the site regularly to check the completeness of patient records, the accuracy of entries on the Case Report Form (CRF), the adherence to the protocol and to Good Clinical Practice (GCP), the progress of enrollment, and to ensure that study investigational product is being stored, dispensed, and accounted for according to specifications. Key study personnel must be available to assist the field monitor during these visits.

The investigator must maintain source documents for each patient in the study, consisting of case and visit notes (hospital or clinic medical records) containing demographic and medical information, laboratory data and the results of any other tests or assessments. All information on CRFs must be traceable to these source documents in the patient's file. The investigator must also keep the original informed consent form signed by the patient (a signed copy is given to the patient).

The investigator must give the monitor access to all relevant source documents to confirm their consistency with the CRF entries. The investigator must give the monitor access to all relevant follow-up source documents for safety monitoring purposes and safety database updates.

4.5. Trial Assessments and Procedures

4.5.1. Screening/Baseline Assessments and Procedures

- Medical history: All patients admitted with secretory diarrhea with severe dehydration will be offered to participate in the study.
- Informed consent. Severely ill patients unable to sign the consent form will be resuscitated according to the proper SOPs, until they are able to make an informed decision regarding the enrollment.
- Randomization and assignment to treatment Group. IP assignment.
- Concomitant medication review.
- Physical examination: height, body weight, temperature, thirst, HEENT (note and record signs of dehydration, such as sunken eyes), skin (note and record signs of dehydration, such loss of turgor), level of consciousness using AVPU (active, response on voice or pain, unconscious) criteria, vomiting.
- Hydration status should be assessed in each participant including assessment of IV fluids, oral ORS intake and oral water intake.
- Vital signs: body temperature, heart rate, respiratory rate, blood pressure (including orthostatic blood pressure measurement when possible), urine output.
- Blood collection (5 ml) for Complete Blood Count (CBC), Basic Metabolic Panel (BMP) including serum electrolytes and creatinine.
- Stool collection for *V. cholerae* RDT (dark field microscopy) and culture.
- Initiate Re-hydration and antibiotic treatment in accordance with the SOPs for cholera patients until recovery.
- Initiate IP administration as soon as participants can tolerate oral intake.

4.5.2. Efficacy Assessments and Procedures

- Medications review.
- Physical examination: Body weight, thirst, HEENT (note and record signs of dehydration, such as sunken eyes), skin (note and record signs of dehydration, such loss of turgor), level of consciousness, vomiting.
- Hydration status should be assessed in each participant including assessment of IV fluids, oral ORS intake and oral water intake. The volume of rehydration solutions received by the participant is recorded continuously for both enteral and parenteral rehydration for the entire duration of the treatment. Access to unaccounted water (i.e. tap water) should be restricted, and measured volume of ORS or water should be provided for free access instead, with the entire volume of consumed liquid measured and recorded in the charts.

- Vital signs: body temperature, heart rate, respiratory rate, blood pressure (including orthostatic blood pressure measurement when possible), and urine output.
- Blood collection (5 ml) for Complete Blood Count (CBC), Basic Metabolic Panel (BMP) including serum electrolytes and creatinine at treatment dose #5.
- Stool collections for efficacy analysis starts immediately after participant receives the first dose of IP and continues for the entire duration of the treatment. Stool samples are collected continuously, and weighed at 12-hour intervals. Number of stool passages and stool weight is recorded in CRFs.
- At the end of the treatment the last physical exam is performed as per the schedule of events and stool sample will be sent for *V. cholerae* culture to confirm elimination of the pathogen. During the pre-treatment and treatment periods the data will be recorded into provided CRFs by the PI or his designee.

4.5.3 Safety Assessments and Procedures

- Physical examination: height, body weight, thirst, HEENT (note and record signs of dehydration, such as sunken eyes), skin (note and record signs of dehydration, such as loss of turgor), level of consciousness, vomiting.
- Vital signs: body temperature, heart rate, respiratory rate, blood pressure (including orthostatic blood pressure measurement when possible), and urine output.
- Clinical Laboratory assessments: Complete Blood Count (CBC), Basic Metabolic Panel (BMP)

Procedures and assessments may be performed as part of the subject's standard medical care; however, data for these assessments should remain in the subject's medical record and should not be provided to HB, unless specifically requested by the sponsor. Laboratory assessments will be done at the on-site laboratories.

Schedule of activities during screening and three days of treatment period is given in appendix 1

4.6. Start of Trial and End of Trial

Trial starts once the participant has signed the informed consent form. The end of trial is defined as database lock after completion of the study by the last patient. A participant is considered to have completed the study if he or she has completed all phases of the study including the last visit or the last scheduled procedure shown in **Appendix I**.

4.7. Adverse Events and Serious Adverse Events

4.7.1. Definitions of AE, SAE and ADR

Terminology according to ICH S2A:

Adverse event: An adverse event (AE) can therefore be any unfavourable and unintended sign (including an abnormal laboratory finding, for example), symptom, or disease temporally associated with the use of a medicinal product, whether or not considered related to the medicinal product.

Adverse Drug Reaction (ADR): In the *pre-approval clinical experience* with a new medicinal product or its new usages, particularly as the therapeutic dose(s) may not be established:

Unexpected Adverse Drug Reaction: An adverse reaction, the nature or severity of which is not consistent with the applicable product information (e.g., Investigator's Brochure for an unapproved investigational medicinal product).

Serious Adverse Event or Adverse Drug Reaction: During clinical investigations, adverse events may occur which, if suspected to be medicinal product-related (adverse drug reactions), might be significant enough to lead to important changes in the way the medicinal product is developed (e.g.,

change in dose, population, needed monitoring, consent forms). This is particularly true for reactions which, in their most severe forms, threaten life or function. Such reactions should be reported promptly to regulators.

Serious adverse event (experience) or reaction is any untoward medical occurrence that at any dose:

** results in death,*

** is life-threatening,*

NOTE: The term "life-threatening" in the definition of "serious" refers to an event in which the patient was at risk of death at the time of the event; it does not refer to an event which hypothetically might have caused death if it were more severe.

** Requires inpatient hospitalisation or prolongation of existing hospitalisation,*

** results in persistent or significant disability/incapacity, or*

** is a congenital anomaly/birth defect.*

4.7.2. Time Period and Frequency for Collecting AE, SAE and ADRs Information

- **Single Cases of Serious, Unexpected ADRs**

All adverse drug reactions (ADRs) that are both serious and unexpected are subject to expedited reporting. This applies to reports from spontaneous sources and from any type of clinical or epidemiological investigation, independent of design or purpose. It also applies to cases not reported directly to a sponsor or manufacturer (for example, those found in regulatory authority-generated ADR registries or in publications). The source of a report (investigation, spontaneous, other) should always be specified.

Expedited reporting of reactions which are serious but expected will ordinarily be inappropriate. Expedited reporting is also inappropriate for serious events from clinical investigations that are considered not related to study product, whether the event is expected or not. Similarly, non-serious adverse reactions, whether expected or not, will ordinarily not be subject to *expedited* reporting.

Information obtained by a sponsor or manufacturer on serious, unexpected reports from any source should be submitted on an expedited basis to appropriate regulatory authorities if the minimum criteria for expedited reporting can be met.

Causality assessment is required for clinical investigation cases. All cases judged by either the reporting health care professional or the sponsor as having a reasonable suspected causal relationship to the medicinal product qualify as ADRs. For purposes of reporting, adverse event reports associated with marketed drugs (spontaneous reports) usually imply causality. Many terms and scales are in use to describe the degree of causality (attributability) between a medicinal product and an event, such as certainly, definitely, probably, possibly or likely related or not related. Phrases such as "plausible relationship," "suspected causality," or "causal relationship cannot be ruled out" are also invoked to describe cause and effect. However, there is currently no standard international nomenclature. The expression "reasonable causal relationship" is meant to convey in general that there are facts (evidence) or arguments to suggest a causal relationship.

- **Other Observations**

There are situations in addition to single case reports of "serious" adverse events or reactions that may necessitate rapid communication to regulatory authorities; appropriate medical and scientific judgement should be applied for each situation. In general, information that might materially influence the benefit-risk assessment of a medicinal product or that would be sufficient to consider changes in medicinal product administration or in the overall conduct of a clinical investigation represents such situations. Examples include:

- a. For an "expected," serious ADR, an increase in the rate of occurrence which is judged to be clinically important.
- b. A significant hazard to the patient population, such as lack of efficacy with a medicinal product used in treating life-threatening disease.
- c. A major safety finding from a newly completed animal study (such as carcinogenicity).

4.7.3. Identifying AE, SAE and ADRs

Principal investigator will be responsible for determining whether an adverse event (AE) is expected or unexpected. An AE will be considered unexpected if the nature, severity, or frequency of the event is not consistent with the risk information previously described for the study intervention. Time period and frequency for event assessment and follow-up:

The occurrence of an adverse event (AE) or serious adverse event (SAE) or adverse drug reaction (ADR) may come to the attention of study personnel during study weeks and interviews of a study participant presenting for medical care, or upon review by a study monitor.

Any medical condition that is present at the time that the participant is screened will be considered as baseline and not reported as an AE. However, if the study participant's condition deteriorates at any time during the study, it will be recorded as an AE. Changes in the severity of an AE will be documented to allow an assessment of the duration of the event at each level of severity to be performed. AEs characterized as intermittent require documentation of onset and duration of each episode.

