4.7.4. Recording AE, SAE and ADRs

All AEs, including local and systemic reactions not meeting the criteria for AE/SAEs/ADRs, will be captured on the appropriate Adverse Event Form. Information to be collected includes event description, time of onset, clinician's assessment of severity, relationship to study product (assessed only by those with the training and authority to make a diagnosis), and time of resolution/stabilization of the event.

All AEs occurring while on study must be documented appropriately regardless of relationship. All AEs will be followed to adequate resolution.

Any medical condition that is present at the time that the participant is screened will be considered as baseline and not reported as an AE. However, if the study participant's condition deteriorates at any time during the study, it will be recorded as an AE.

Changes in the severity of an AE will be documented to allow an assessment of the duration of the event at each level of severity to be performed. AEs characterized as intermittent require documentation of onset and duration of each episode.

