
diarrhea following VR-AD-1005 administration.
 
 • Evaluation of safety and tolerability of VR-AD-1005 in addition to standard of care (SoC) versus SoC with placebo in adults with symptomatic cholera via documentation of adverse events, physical examination, and vital signs. 	
the treatment for both treatment groups.
 
 • Time until clinical recovery (defined as disappearance of watery stool and two consecutive passages of soft stool). Duration of diarrhea until the passage of first non-watery stool (soft/loose) or no stool for 12 hours or the end of treatment (72 hours) will be derived from date and time records in daily stool charts. • Number of subjects with clinical recovery as above within treatment group. The number of subjects with clinical recovery will be recorded as total for the entire treatment duration, and as number of recoveries per each 24-hour period of treatment. • Number of unscheduled IV rehydration episodes per treatment. The number of unscheduled IV rehydration episodes per treatment will be recorded for the entire duration of the treatment. Unscheduled IV rehydration is defined as "receipt of IV fluid during the maintenance phase of hydration due to development of severe dehydration or some dehydration with high purging (>15 ml/kg/hour) or persistent vomiting (>3 episodes/hour), or failure to take ORS for any reason" • Duration of IV rehydration for the entire treatment period per treatment group and per each 24- hour period of treatment. • Safety will be measured by the proportion of patients that will present with AE/SAE as defined in Appendix II following administration of VR-AD- 1005. 	
measure of hydration status of the participants, as well as providing a measure of the duration of the illness. Dehydration is the primary cause of death in cholera; duration of illness is the primary measure of the burden on the healthcare system and quality of life/productivity loss for cholera patients. Assessment of reduction in the need for unscheduled intravenous rehydration and time until switch to oral rehydration therapy will allow to assess the benefit of VR-AD-1005 for in-patient management of cholera cases. Thus, secondary end-points allow to characterize the benefits related to potential improvements in the clinical course of the disease, case management and quality of life for cholera patients.

---	--	--

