6.4. Safety Analyses

Safety analysis is not the primary or secondary objective of this study, thus safety will be analyzed as summary statistics during treatment. AEs will be coded per Medical Dictionary for Regulatory Activities (MedDRA), and calculated. Each AE will be counted once only for a given participant, and presented using standard available criteria for severity, frequency, and relationship of AEs to study intervention. Start date, stop date, severity, relationship, expectedness, outcome, and duration will be reported for each SAE. Adverse events leading to premature discontinuation from the study intervention and serious treatment-emergent AEs will be listed. Proportion of the patients presented with AE or SAE will be calculated for IP and Placebo arms as a fraction of the total number of participants per arm and expressed as percent. Percentage of AE and SAE occurrence will be compared between IP and placebo groups to provide information regarding the safety of the investigational product.

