Appendix II : ADVERSE EVENTS AND SERIOUS ADVERSE EVENTS – DEFINITIONS, SEVERITY, AND CASUALTY

Definitions

Adverse event: An untoward medical occurrence after exposure to a medicine, which is not necessarily caused by that medicine.

Serious Adverse event: An adverse reaction that results in death, is life-threatening, requires hospitalisation or prolongation of existing hospitalisation, results in persistent or significant disability or incapacity, or is a birth defect

Assessment of severity

The terms "severe" and "serious" are not synonymous. Severity refers to the intensity of an adverse event (rated as mild, moderate, or severe, or according to a pre-defined grading criterion; the event itself may be of relatively minor medical significance (such as severe headache without any further findings).

Severity and seriousness need to be independently assessed for each adverse event recorded on the CRF.

Serious adverse events are required to be reported by the Investigator to the Sponsor immediately (i.e., no more than 24 hours after learning of the event).

The assessing adverse event severity table below will be used for assessing severity for adverse events.

Table -Adverse Event Severity Grading Scale

Grade	Severity
1	Mild; asymptomatic or mild symptoms; clinical or diagnostic observations only; or intervention not indicated
2	Moderate; minimal, local, or non-invasive intervention indicated; or limiting age-appropriate instrumental activities of daily living ^a
3	Severe or medically significant, but not immediately life-threatening; hospitalization or prolongation of hospitalization indicated; disabling; or limiting self-care activities of daily living ^b
4	Life-threatening consequences or urgent intervention indicated ^d
5	Death related to adverse event ^d

Note:

^a Instrumental activities of daily living refer to preparing meals, shopping for groceries or clothes, using the telephone, managing money, etc.

^b Examples of self-care activities of daily living include bathing, dressing and undressing, feeding oneself, using the toilet, and taking medications, as performed by patients who are not bedridden.

^c If an event is assessed as a "significant medical event," it must be reported as a serious adverse event

^d Grade 4 and 5 events must be reported as serious adverse events

Assessment of causality

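### The AE/SAE percentage compared between arms does not separate worsening cholera from other events, so a drug effect on the disease can dilute or offset drug-caused AEs in it

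*Combined protocol and SAP*

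**What the plan says.** **Recording.** Sections 4.7.3 and 4.7.4 give the same rule. The starting point is "Any medical condition that is present at the time that the participant is screened will be considered as baseline and not reported as an AE". The exception follows: if a participant's "condition deteriorates at any time during the study, it will be recorded as an AE". Section 4.7.4 adds: "All AEs occurring while on study must be documented appropriately regardless of relationship". Neither section sets the index cholera episode apart.

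**Safety endpoint.** Table 1 in Section 5.0 states: "Safety will be measured by the proportion of patients that will present with AE/SAE as defined in Appendix II". Section 6.0 repeats this for AEs. Section 6.4 takes each arm's percentage of all its participants and says: "Percentage of AE and SAE occurrence will be compared between IP and placebo groups". It also plans MedDRA coding and presentation by severity, frequency and relationship. No test, margin or power is given for safety. Section 6.4 says that safety is neither a primary nor a secondary objective, while Table 1 lists it among the secondary ones.

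**Efficacy endpoint on the same event.** Unscheduled IV rehydration covers IV fluid given in the maintenance phase "due to development of severe dehydration or some dehydration with high purging", among other reasons (Table 1; Sections 6.0 and 6.3).

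**Seriousness.** Section 4.7.1 makes prolonged hospitalisation and threat to life serious for any untoward occurrence. Appendix II defines a serious event more narrowly, as a reaction, but its footnote requires Grade 4 and 5 events to be reported as serious. Grade 4 reads: "Life-threatening consequences or urgent intervention indicated".

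**The concern.** The trial is meant to show that the drug reduces fluid loss. If it does, renewed dehydration and similar worsening should be rarer on active. Where worsening is recorded as an AE, the safety percentage contains a component that moves with efficacy. A fall in that component can cancel part or all of a rise in drug-caused AEs. The distortion favours the drug when it works, which is when its safety matters most for further development. If the drug has no effect on the disease, worsening events mainly dilute the comparison.

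The plan specifies no analysis that separates the two kinds of event. It also does not say when a relapse counts as deterioration, so that decision is left to each investigator.

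**Working it through.** **The plan's own figures.** The documents give no rate of AEs, SAEs or cholera worsening, so there is no safety figure to reproduce. The only computed design figure is the power of the stool-output t-test in Section 5.0. With a difference of 0.33 × 280 = 92.4 g/kg, SD 156 and two-sided 5%, the noncentral t gives 0.835 at 50 per arm (stated 0.82) and 0.950 at 75 per arm (stated 0.94). That is close enough, but it concerns efficacy. Only the 33% is borrowed below.

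**Inputs for the illustration**
- Relative fall in progression AEs on active: 33%. This is the Section 5.0 stool effect applied to the progression rate, which is an assumption.
- Placebo progression rate d: 10% to 40%, assumed.
- Other AEs: 5% placebo, 20% active, assumed.
- Progression and other AEs independent, assumed.

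**Formula**
- Placebo, any AE: 1 - (1 - d) × 0.95
- Active, any AE: 1 - (1 - 0.67d) × 0.80

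| d (placebo) | Active progression | Any AE, placebo | Any AE, active | Difference (points) |
|---|---|---|---|---|
| 10% | 6.7% | 1 - 0.900 × 0.95 = 14.5% | 1 - 0.933 × 0.80 = 25.4% | +10.9 |
| 20% | 13.4% | 1 - 0.800 × 0.95 = 24.0% | 1 - 0.866 × 0.80 = 30.7% | +6.7 |
| 30% | 20.1% | 1 - 0.700 × 0.95 = 33.5% | 1 - 0.799 × 0.80 = 36.1% | +2.6 |
| 40% | 26.8% | 1 - 0.600 × 0.95 = 43.0% | 1 - 0.732 × 0.80 = 41.4% | -1.6 |

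Excluding progression, the difference is 20% - 5% = +15 points in every row. The any-AE difference simplifies to 0.15 - 0.414d, which reaches zero at d = 0.15 / 0.414 = 36%.

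**Break-even.** Suppose both arms share the same background of other AEs and the drug adds toxicity t, independently. The arms then have equal any-AE percentages when t = 1 - (1 - d) / (1 - 0.67d). For d of 10%, 20%, 30%, 40% and 50%, t is 3.5%, 7.6%, 12.4%, 18.0% and 24.8%. Smaller toxicity than this shows as a difference in the drug's favour.

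**A second case.** With d = 30%, background 10% and t = 10%, any AE is 1 - 0.70 × 0.90 = 37.0% on placebo and 1 - 0.799 × 0.90 × 0.90 = 35.3% on active. Excluding progression, it is 10.0% and 1 - 0.90 × 0.90 = 19.0%.

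**The case against.** The strongest reply is that the plan already separates events in other ways. The AE form records relationship to study product (Section 4.7.4), and Appendix II tells investigators to weigh the event's known association with the disease. Section 6.4 plans MedDRA coding and display by relationship. Specific toxicity could therefore still be seen, and a reader who infers that the plan hides drug harm altogether goes too far: the problem lies in the aggregate percentage. What remains is that this percentage is the named endpoint and the between-arm comparison. A case-by-case yes/no causality call is also not the same as a prespecified rule for cholera progression.

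A reader might also infer that worsening cholera will often be an SAE. The documents do not support that. They give no frequency. IV replacement for high purging or persistent vomiting is part of standard care (Section 4.9), so it is not plainly a Grade 4 event. Everyone stays in hospital for the three treatment days (Section 4.3), so a relapse in that window does not by itself prolong the stay. The serious-event definitions in Section 4.7.1 and Appendix II differ. Some worsening can become an SAE, and no more can be said.

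The overlap with the efficacy endpoint is itself uncertain. All participants enter severely dehydrated (Section 4.2.3), and whether relapse after rehydration is deterioration from the screening state is undefined. Unscheduled IV fluid also includes failure to take ORS for any reason, which need not be worsening. This limits what can be claimed about size, but it also argues for a written rule.

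Finally, safety is summarised without a planned test, so a loss of power is not a property of this plan. At 10% to 20% placebo progression in the first illustration, the excess is diluted but still visible.

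**Conclusion.** The concern holds for the aggregate percentage. As written, worsening of the index cholera episode can be recorded as an AE and in some cases become an SAE, and the safety summary compares the undivided percentage by arm. A beneficial effect on the disease can therefore dilute or offset drug-caused AEs in that figure, and the other planned displays reveal this only in part.

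The size is unknown. Under the first set of assumptions, a true 15-point excess shrinks by about 4 points at 10% placebo progression, and it reverses slightly at 40%. These results depend on assumed AE rates, on independence, on carrying the 33% stool effect over to progression, and on relapses actually being recorded as AEs.

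It would be tempting to conclude that the safety endpoint should exclude progression. The documents do not support that step. Drug harm could itself appear as worse purging, and Section 4.7.2 names lack of efficacy in life-threatening disease as a significant hazard. A supplementary comparison is justified; a replacement is not. This is a cheap improvement to the analysis plan.

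**What to change.** Keep AE recording, expedited reporting and the all-event AE/SAE comparison unchanged, with the last remaining the safety endpoint. Then:

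1. In Section 6.4, prespecify criteria for events that are progression of the index cholera episode, including how a relapse after initial rehydration is classified.
2. Flag these events on the AE form, blind to arm.
3. Report AE and SAE proportions by arm excluding flagged events, and for flagged events alone, beside the all-event figures.
4. Reconcile the serious-event definitions in Section 4.7.1 and Appendix II, and the status of safety in Table 1 and Section 6.4.

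The cost is one field on the AE form and additional rows or one table in the report. The downside is a blinded classification judgement. The table excluding progression must not be read alone, because drug harm could appear as progression; showing all three sets of figures together limits that risk.
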